## 15.2. Appendix 2: Continual Reassessment Method Details

The nominal doses used in the continual reassessment method, the  $\hat{x}$ -hats, will be derived as:

$$\hat{x}_i = \log \left( \frac{d_i}{d_{ref}} \right)$$

Where  $d_1 = 2$ ,  $d_2 = 6$ ,  $d_3 = 10$  and  $d_{ref} = 6$ . The  $d_i$  correspond to the amount of DTX401 administered at each dose level, in units of  $10^{12}$  genome copies/kg.

A logistic model will be used to model the dose-toxicity curve. Let

$$Y_i = \begin{cases} 0 & \text{if the } i\text{th subject does not experience a DLT} \\ 1 & \text{otherwise} \end{cases}$$

Then

$$p(Y = 1 | \hat{x}_i, \alpha, \beta) = \frac{e^{\alpha + \beta \hat{x}_i}}{1 + e^{\alpha + \beta \hat{x}_i}}$$

The joint distribution of  $\alpha$  and  $\beta$  is given by

$$\begin{pmatrix} \alpha \\ \log \beta \end{pmatrix} \sim N \left( \begin{pmatrix} \mu_\alpha \\ \mu_\beta \end{pmatrix}, \begin{pmatrix} \sigma_\alpha \times \sigma_\alpha & \sigma_\alpha \times \sigma_\beta \times \rho \\ \sigma_\alpha \times \sigma_\beta \times \rho & \sigma_\beta \times \sigma_\beta \end{pmatrix} \right)$$

Initial (prior) values  $\mu_\alpha = -2.3097$ ,  $\log \mu_\beta = -0.4323$ ,  $\sigma_\alpha = 1.6604$ ,  $\log \sigma_\beta = 0.0044$  and  $\rho = -0.2405$  are used based on simulations.

The estimate of the maximum tolerated dose will be the highest dose for which the full Bayes posterior estimate of  $p(\text{DLT} | d_i)$  is strictly less than or equal to the target toxicity rate.

[figure not shown]
A dose is cleared if it is either  $2 \times 10^{12}$  genome copies/kg or if it is no more than 1 dose level higher than the highest dose at which at least 3 subjects have been treated.

[figure not shown]
[figure not shown]
**15.3. Appendix 3:** 

Please respond to each question or statement by marking one box per row.

A large, solid black rectangular area covering the majority of the page, indicating that the content has been redacted.

**15.4. Appendix 4:** 

[Redacted]

[figure not shown]
[Redacted]

[figure not shown]
[Redacted]

[figure not shown]
[Redacted]

[figure not shown]

[figure not shown]

[figure not shown]

[figure not shown]
**15.6. Appendix 6: Glycogen Storage Disease Type Ia (GSDIa) Morning Diary**

[figure not shown]

[figure not shown]
**15.7. Appendix 7: Glycogen Storage Disease Type Ia (GSDIa) Evening Diary**

[figure not shown]

[figure not shown]

**15.8. Appendix 8:** 

**15.9. Appendix 9:**

STATISTICAL ANALYSIS PLAN (SAP)

Title: A Phase 1/2, Open-Label Safety and Dose-Finding Study of

Adeno-Associated Virus (AAV) Serotype 8 (AAV8)-Mediated Gene Transfer of Glucose-6-Phosphatase (G6Pase) in Adults

with Glycogen Storage Disease Type Ia (GSDIa)

Protocol: 401GSDIA01

Investigational Product: DTX401 (Nonreplicating, recombinant AAV8 vector that

contains a codon-optimized, human G6PC coding sequence)

Phase: 1/2

Sponsor: Ultragenyx Pharmaceutical Inc.

[name]

[name]

Author:

Senior Director, Biostatistics, Biometrics

Director, Biostatistics, Biometrics

Date: 12 July 2021

Date Amended: 04 March 2022

Version Number: Version 2.0

CHANGE HISTORY

Version	Changes and Rationale for Changes
1.0	Initial Version
2.0	Minor changes in the document include changes to match the language in the SAP with the corresponding language in the protocol, removing redundancy in analyses that were described multiple times in the document, and adding clarifications around endpoint or analysis.
	Major changes in the document are summarized below.
	Section 3.7:
	Added update on latest data monitoring committee (DMC) conducted for the study
	 Removed text about the roles and responsibilities of the DMC because that is outside the scope of the SAP.
	Section 8.4.1: Added derivation of actual dose administered to the subject
	Section 8.5.1: Added summary of cornstarch used and amount of carbohydrates in the dinner prior to controlled fasting challenge (CFC) upon request from medical monitor to understand use of these quantities in CFC.
	Section 8.5.2 : Added analysis window for analysis of cornstarch data. Added plot for daytime, bedtime, and nighttime frequency of cornstarch doses.
	Section 8.5.3:
	 Added exploratory analyses of continuous glucose monitoring (CGM) data based on the request from medical monitor of the study to gain better understanding of this data.
	 Added derivation for percentage of time spent in any glucose range in a week
	 Removed text about the use of both Cenduit and Clarity data for analysis of CGM data because Clarity data will not be part of clinical dataset.
	Section 8.6.7: Removed reference of few safety labs parameters from this section because analyses planned for these parameters are already described in other sections. Further, clarified that this section focuses on analyses for lab parameters collected at the central lab.

APPEND	IX 1. SCHEDULE OF EVENTS	30
APPEND	IX 2. CONTINUAL REASSESSMENT METHOD DETAILS	36
APPEND	IX 3.	37
APPEND	IX 4.	40
APPEND	IX 5.	41
APPEND	IX 6. GLYCOGEN STORAGE DISEASE TYPE IA (GSDIA) MORNING DIARY	47
APPEND	IX 7. GLYCOGEN STORAGE DISEASE TYPE IA (GSDIA) EVENING DIARY	48
APPEND	IX 8.	53
APPEND	IX 9.	54
	LIST OF TABLES	
Table 1:	Numerical Scoring of Adult Domains	15
Table 2:	Central Clinical Laboratory Parameters	25

LIST OF ABBREVIATIONS

Abbreviation	Definition
AAV8	adeno-associated virus serotype 8
AE	adverse event
ALT	alanine aminotransferase
BMI	body mass index
CRF	case report form
CRM	continual reassessment method
CGM	continuous glucose monitoring
CSR	clinical study report
CTCAE	Common Terminology Criteria for Adverse Events
DLT	dose-limiting toxicity
DMC	data monitoring committee
ECG	electrocardiogram, electrocardiographic
eCRF	electronic case report form
G6P	glucose-6-phosphate
G6Pase	glucose-6-phosphatase (protein)
G6PC	glucose-6-phosphatase (gene)
GC	genome copies
GSDIa	glycogen storage disease type Ia
IgG	immunoglobulin G
IV	intravenous
MedDRA	Medical Dictionary for Regulatory Activities
MTD	maximum tolerated dose
NCI	national cancer institute
OBD	optimal biological dose
PDFF	proton density fat fraction
PT	preferred term

Abbreviation	Definition
QTc	QT interval corrected for heart rate
SAE	serious adverse event
SAP	statistical analysis plan
SOC	system organ class
TEAE	treatment-emergent adverse event
ULN	upper limit of normal

1. INTRODUCTION

The purpose of this Statistical Analysis Plan (SAP) is to provide details of the statistical analyses that have been outlined within the 401GSDIA01 original Protocol dated 17 May 2017, Protocol Amendment 1 dated 13 December 2017, Amendment 2 dated 02 March 2018, Amendment 3 dated 18 February 2019, Amendment 4 dated 10 September 2019, Amendment 5 dated 28 October 2019, and Amendment 6 dated 16 February 2021.

2. STUDY OBJECTIVE(S)

2.1. Primary Objective

• To determine the safety of single intravenous (IV) doses of DTX401 in adults with GSDIa, including the incidence of dose-limiting toxicities (DLTs).

2.2. Secondary Objective

- To establish a dose of DTX401 that achieves symptom-free euglycemia (glucose ≥54 mg/dL [≥3.0 mmol/L])* in a setting of a controlled fasting challenge to allow further clinical development.
 - * Following protocol amendment 6, the definition of euglycemia for the end of the controlled fasting challenge changed from ≥60 mg/dL (≥3.3 mmol/L) to ≥54 mg/dL (≥3.0 mmol/L)

2.3. Exploratory Objectives

3. STUDY DESIGN

3.1. Study Overview

401GSDIA01 is a Phase 1/2, open-label, single-arm, multicenter, safety and dose-finding study to determine the safety, tolerability, and efficacy of DTX401 in adults with GSDIa.

3.2. Dosage and Administration

DTX401 will be administered as a single peripheral IV infusion. The following doses will be evaluated using a continual reassessment method (CRM) to estimate the maximum tolerated dose (MTD):

- **Dose 1**: 2.0×10^{12} genome copies (GC)/kg
- **Dose 2**: 6.0×10^{12} GC/kg
- **Dose 3**: 1.0×10^{13} GC/kg

Eligible subjects may be enrolled into 1 of the following cohorts of 3 subjects each and receive a single IV infusion of DTX401.

- Cohort 1: Dose 1 $(2.0 \times 10^{12} \text{ GC/kg})$ with a reactive steroid regimen (prednisone starting dose of 40 mg/day)
- Cohort 2: Dose 2 $(6.0 \times 10^{12} \text{ GC/kg})$ with a reactive steroid regimen (prednisone starting dose of 40 mg/day)
- Cohort 3: Dose 2 $(6.0 \times 10^{12} \text{ GC/kg})$ with an optimized reactive steroid regimen (prednisone starting dose of 60 mg/day)
- Cohort 4: Dose 2 (6.0×10^{12} GC/kg) with a prophylactic steroid regimen

A cohort may be expanded to include additional subjects to confirm the findings for the cohort.

Subjects in Cohorts 1 and 2 were dosed at a minimum of 2 weeks (14 days) apart. Subjects in subsequent cohorts will be dosed at a minimum of 1 week (7 days) apart.

After the third patient in a cohort reaches the 12-week time point, the CRM will propose a dose for the next cohort using the collected data from the previous cohort. The decision to proceed will be made after the data monitoring committee (DMC) has evaluated at least 12 weeks of safety data for all subjects in a dosing cohort.

Subjects will be followed for 52 weeks following DTX401 administration. After completion of the Week 52 visit or early withdrawal, subjects will be offered enrollment in a 4-year extension study to evaluate the long-term (a total of 5 years) safety and efficacy of DTX401.

3.3. Blinding and Randomization Methods

Not applicable.

3.4. Stratification Factors

Not applicable.

3.5. Sample Size Considerations

Simulations show that if all 3 doses are safe and no DLTs occur, the CRM will recommend dose escalation to 1×10^{13} GC/kg (genome copies measured by and the recruitment of 12 subjects. Based on safety and efficacy observations in Cohorts 1, 2, and 3 (3 subjects each) and a positive recommendation from the DMC, it was decided to enroll a fourth cohort of 3 subjects. The planned sample size of the study will therefore be 12 subjects including 4 cohorts.

3.6. Interim Analysis

No interim analyses were performed.

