hepatitis and treated with corticosteroids if needed (Section 8.2.6.2), having an interval of more than 14 days between subjects in Cohorts 1 and 2 and more than 7 days between subjects in subsequent cohorts does not change either safety evaluations or the medical management of study subjects. To date, no related serious adverse events (SAEs) or DLTs have been reported for DTX401. Consistent with previous experience (Manno et al., 2006; Nathwani et al., 2011b; Nathwani et al., 2014), mild, transient, asymptomatic increases in liver aminotransferase levels have been observed following DTX401 administration that resolved with steroids (Derks et al., 2019; Weinstein et al., 2019).

Subject safety will be closely monitored throughout the study, including assessment of hypoglycemic events, frequent monitoring of liver enzymes, and inpatient observation following dosing and at multiple time points throughout the 52-week study duration.

For Cohorts 1 and 2, there was a minimum of 12 weeks (84 days) between dosing of the last subject in a dosing cohort and the first subject in the next dosing cohort. After all subjects in Cohorts 1 and 2 completed Week 12, the continual reassessment method (CRM) proposed a dose for the next cohort using the collected data from the previous cohort. The DMC met to review safety data (ie, AEs/SAEs, physical examination findings, vital sign measurements, electrocardiogram [ECG] results, and clinical laboratory assessments [including assessment of liver function]) and provide a recommendation for progressing to the next dosing level (Section 9.3). The CRM will be used for dose escalation to estimate the maximum tolerated dose (MTD) of DTX401 (Section 10.2.1).

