However, further analysis and review of fasting challenge data after changing the prefasting cornstarch dose to 5g showed significantly lower fasting times in cohorts 2 (W52 and W78) and 3 (W24, W32 and W52). In most instances, low post-prandial levels of blood glucose associates, persistence of high circulating insulin levels, and slow cortisol response to hypoglycemia make it challenging to interpret these results. Available CGM recordings have shown an absence of nocturnal hypoglycemia in these subjects despite an overall reduced frequency and total amount of cornstarch. The reason that several subjects can now sleep through the night at home without experiencing hypoglycemia in the absence of cornstarch consumption, but have shorter time to hypoglycemia during the inpatient fasting challenge is unclear. It could be attributed to the artificial threshold of 60 mg/dL for stopping the fasting challenge. This threshold may not allow adequate glucose release to be induced in subjects with higher insulin and lower cortisol levels. In the home setting, subjects clearly do better as their glucose release seems to be better induced, thereby preventing their glucose levels from falling to dangerous levels.

With Protocol Amendment 6, the dinner meal will be personalized for each subject, and will include a target carbohydrate range and overall composition in protein, fats and dietary fibers that is as close as possible to the subject's most current dinner prescription but not higher than the carbohydrate content of the dinner consumed at their baseline fasting challenge. The prefasting cornstarch dose and time of consumption will be per the respective subject's most recent cornstarch prescription and daily regimen at home. In addition, the threshold for stopping the test was lowered to 54 mg/dL (3.0 mmol/L) or when the subject experiences signs and symptoms of hypoglycemia. The new threshold is justified by the fact that signs and symptoms of hypoglycemia associated with an adrenergic reaction and cerebral glucopenia and most physiological hormonal and metabolic responses responses to hypoglycemia may not occur in GSDIa subjects until they reach these levels of blood glucose values. CGM recording during the fasting test will provide continuous glucose measurement data that will allow Investigators to closely monitor subjects when they reach the lower range of blood glucose (ie, below 60 mg/dL).

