### 3. INVESTIGATIONAL PLAN

#### 3.1. Study Overview

Study 401GSDIA01 is a Phase 1/2, open-label, single-arm, multicenter, safety and dose-finding study to determine the safety, tolerability, and efficacy of DTX401 in adults with GSDIa. The primary objective of the study is to determine the safety of single IV doses of DTX401, including the incidence of DLTs. The secondary objective of the study is to establish a dose of DTX401 that achieves symptom-free euglycemia (glucose  $\geq 54$  mg/dL [ $\geq 3.0$  mmol/L]) in a setting of a controlled fasting challenge to allow further clinical development.

DTX401 will be administered as a single peripheral IV infusion. The following doses (per kilogram of body weight) may be evaluated using a CRM to estimate the MTD of DTX401:

- **Dose 1:**  $2.0 \times 10^{12}$  GC/kg
- **Dose 2:**  $6.0 \times 10^{12}$  GC/kg
- **Dose 3:**  $1.0 \times 10^{13}$  GC/kg

Eligible subjects may be enrolled into 1 of the following cohorts of 3 subjects each and receive a single IV infusion of DTX401.

- **Cohort 1:** Dose 1 ( $2.0 \times 10^{12}$  GC/kg) with a reactive steroid regimen (prednisone starting dose of 40 mg/day)
- **Cohort 2:** Dose 2 ( $6.0 \times 10^{12}$  GC/kg) with a reactive steroid regimen (prednisone starting dose of 40 mg/day)
- **Cohort 3:** Dose 2 ( $6.0 \times 10^{12}$  GC/kg) with an optimized reactive steroid regimen (prednisone starting dose of 60 mg/day)
- **Cohort 4:** Dose 2 ( $6.0 \times 10^{12}$  GC/kg) with a prophylactic steroid regimen

A cohort may be expanded to include additional subjects to confirm the findings for the cohort.

Subjects in Cohorts 1 and 2 were dosed at a minimum of 2 weeks (14 days) apart. Subjects in subsequent cohorts will be dosed at a minimum of 1 week (7 days) apart.

For Cohorts 1 and 2, there was a minimum of 12 weeks (84 days) between dosing of the last subject in a dosing cohort and the first subject in the next dosing cohort. After the third subject in each cohort reached the 12-week time point, the CRM (Section 10.2.1) proposed a dose for the next cohort using the collected data from the previous cohort. The decision to proceed was made after the DMC evaluated at least 12 weeks of safety data for all subjects in the dosing cohort, as outlined in the DMC charter (Section 9.3). There were no intracohort dose escalations.

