#### **10.2.6. Interim Analysis**

An interim analysis will be conducted when a minimum of 12-week data are available for all subjects from at least 2 dosing cohorts. Additional interim analyses may be conducted at the Sponsor’s discretion. Results and their dissemination will be at the Sponsor’s discretion. A detailed plan for the analysis of the safety and efficacy data will be presented in the SAP.

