9. CHANGES TO ANALYSES SPECIFIED IN PROTOCOL

None

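### SAP 3.6 and SAP 9 cannot both stand beside the protocol's committed interim analysis, and the SAP omits that the fasting test was changed after fasting results had been reviewed

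*SAP*

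**What the plan says.** **Interim analysis.** Protocol Section 10.2.6, like the synopsis, says: "An interim analysis will be conducted when a minimum of 12-week data are available for all subjects from at least 2 dosing cohorts". Only further interim analyses are left to the sponsor's discretion. The same section adds: "A detailed plan for the analysis of the safety and efficacy data will be presented in the SAP". SAP Section 3.6 consists of one sentence: "No interim analyses were performed". Under the heading "CHANGES TO ANALYSES SPECIFIED IN PROTOCOL", the whole entry in SAP Section 9 is the word None.

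**Reviews of accumulating data.** Protocol Sections 1.3.1 and 3.1 report that the fasting challenge was first modified after the DMC reviewed Cohort 2 Week 12 data. They then report that "further analysis and review of fasting challenge data after changing the prefasting cornstarch dose to 5g showed significantly lower fasting times" in Cohort 2 (Weeks 52 and 78) and Cohort 3 (Weeks 24, 32 and 52). Amendment 6 follows in the text, with a personalised dinner, cornstarch by prescription and a stopping threshold lowered from 60 to 54 mg/dL. SAP Section 3.5, repeating protocol Section 10.2.2, explains the fourth cohort this way: "Based on safety and efficacy observations in Cohorts 1, 2, and 3", together with a favourable DMC recommendation.

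**What the SAP discloses.** Footnotes in SAP Sections 2.2 and 4.2 record that Amendment 6 changed the threshold. SAP Section 3.7 describes the DMC safety reviews, and Section 8.1.1 describes the CRM.

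**The concern.** Time to hypoglycaemia in the controlled fasting challenge is the only secondary endpoint. The secondary objective uses it to choose a dose for further development. With three subjects per cohort, a reader has to know which data were seen before which change to the test.

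A study report that follows SAP Sections 3.6 and 9 would say that there was no interim analysis and no departure from the protocol. It would show fasting times by cohort and in an overall column, as SAP Section 8.1 provides. It would not say that the meal, the cornstarch and the threshold were revised after fasting results had been looked at.

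**Working it through.** No figure in the plan turns on this point, so the check sets the passages side by side.

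**1. Was the trigger for the interim analysis met?** Protocol 10.2.6 needs at least 2 cohorts with at least 12 weeks of data. SAP 3.7 says the DMC had reviewed data to Week 52 for Cohorts 1 to 3 and to Week 24 for Cohort 4. That is 4 cohorts, each with at least 24 weeks. The trigger had passed before SAP version 2.0 (4 March 2022).

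**2. Can the three statements all hold?**

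| What happened to the 10.2.6 analysis | SAP 3.6 (none performed) | SAP 9 (no changes) |
|---|---|---|
| Performed | False | Could hold on this item |
| Not performed | True | False: an analysis in the protocol's statistical section was dropped |

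At least one SAP statement is wrong in either case.

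**3. Which reviews preceded which changes?**

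| Review (protocol 1.3.1, 3.1, 10.2.2) | Change that followed | In the SAP? |
|---|---|---|
| DMC review of Cohort 2 Week 12 data | Dinner carbohydrate from 20–30 g to 15–20 g; cornstarch from 35 g to 5 g | Not mentioned |
| Fasting data, Cohorts 2 and 3 | Amendment 6: dinner, cornstarch, threshold from 60 to 54 mg/dL | Threshold change footnoted; the review is not mentioned |
| Safety and efficacy observations, Cohorts 1 to 3 | Cohort 4 enrolled | Yes, SAP 3.5 |

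The protocol does not say whether fasting times were part of the first review, nor who carried out the second. Week 78 lies beyond this study's Week 52 end, and Week 32 is not a scheduled challenge visit, so the source of those data also needs stating.

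**4. How much of the study had been seen?** The plan is 4 cohorts × 3 = 12 subjects. Before Amendment 6, fasting data had been reviewed from 2 × 3 = 6 of 12. The Cohort 4 decision used 3 × 3 = 9 of 12. Amendment 6 is dated 16 February 2021; SAP version 1.0 (12 July 2021) came 146 days later and version 2.0 came 381 days later. The review could therefore have been recorded in the SAP.

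**5. Do test versions mix within a subject?** Cohort 2 had completed Week 12 before the first modification, so its baseline and Week 12 tests used the 35 g version. The protocol places its Week 52 tests after the move to 5 g. The Cohort 2 change from baseline at Week 52 therefore compares two versions of the test.

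**6. Is the event definition the same throughout?** Protocol 10.2.3.1 and SAP 4.2 use <54 mg/dL. SAP 8.5.1, which governs the analysis, uses <60 mg/dL. SAP 9 does not list the difference.

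**The case against.** The strongest reply is that little is hidden. The SAP footnotes the threshold change twice, gives the efficacy basis for Cohort 4, and describes the DMC and CRM processes. Section 8.5.1 also summarises pre-test cornstarch and dinner carbohydrate by visit. The reason for the Amendment 6 changes stands at length in the protocol. This is a fair reply and it limits the point. It does not repair the contradiction between Sections 3.6, 9 and 10.2.6, and it does not put the fasting-data review into the SAP.

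Several stronger readings are tempting, but the documents do not support them:

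- *The endpoint would be reported as fully pre-specified.* The SAP nowhere claims this, and its footnotes say that the definition changed. What is missing is that the changes followed a review of fasting data.
- *CRM updates and DMC reviews were undeclared interim analyses.* Protocol 3.1 says openly that the CRM "proposed a dose for the next cohort using the collected data from the previous cohort". These steps are the planned dose-finding process and SAP 3.7 and 8.1.1 describe them.
- *Repeated looks inflate a false-positive rate.* No hypothesis test, alpha or success rule exists for this endpoint; it is only summarised.
- *The lower threshold adds a calculable number of minutes.* The documents give no rate of glucose decline. The endpoint is a change from baseline, so a shift common to both tests would largely cancel. SAP 8.5.1 still uses <60 mg/dL. The symptom stop and the baseline caps on carbohydrate and cornstarch in protocol 8.1.1 could shorten times.
- *Only Cohorts 1 to 3 are affected.* The reviewed tests had already been run when the threshold changed. The new conditions act on later tests, which would chiefly mean Cohort 4.
- *Efficacy data alone drove Cohort 4.* Protocol 3.1 gives a safety trigger: inadequate control of aminotransferase elevations in Cohort 3.

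**Conclusion.** The point holds as a documentation fault with consequences for interpretation. At least one of SAP 3.6 and SAP 9 is false. SAP 9 is also incomplete on the event definition, whatever happened to the interim analysis. The SAP leaves out that changes to the test behind the only secondary endpoint followed review of fasting results from 6 of 12 planned subjects.

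This rests on the protocol's own past-tense account and on cohorts of exactly three subjects. It does not rest on any claim that results are biased by a known amount, and no error rate can be attached to it. The correction should be made before reporting, because fasting time informs the choice of dose.

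**What to change.** - **SAP 3.6:** state whether the protocol 10.2.6 interim analysis was performed or dropped. List each review of fasting or efficacy data (Cohort 2 Week 12; Cohorts 2 and 3 before Amendment 6; Cohorts 1 to 3 before Cohort 4), with the data seen, who saw them and what changed. Refer to Sections 3.7 and 8.1.1 for the planned DMC and CRM steps.
- **SAP 9:** replace None with the outcome for the interim analysis and with the difference between SAP 8.5.1 (<60 mg/dL) and protocol 10.2.3.1 (<54 mg/dL). The sponsor must reconcile these passages; no view is taken here on which value is right.
- **SAP 8.5.1:** label fasting-time results in all four cohorts and in the overall column by the test version used at baseline and at follow-up. Call them exploratory because the test was changed after fasting results were reviewed, and state that no claim of significance will be made.

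The cost is SAP text and table footnotes, with no new data or subjects. Flags in the existing tables are enough, since splitting cohorts of three further would leave very small cells. The drawback for the sponsor is a more modest description of how far the fasting-time evidence was planned in advance.
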